5.3.3.5 Overall Survival and Intubation and Mechanical Ventilation Free Survival

Overall survival (OS) is defined as the time in days from randomization until death by any cause.

Intubation and mechanical ventilation free survival (IMVFS) is defined as the time in days from randomization until the earliest event of death by any cause or requirement for intubation and/or mechanical ventilation as indicated by the first occurrence of a WHO OSCI score of 6 or above.

Participants who complete the 42-day study period or prematurely withdraw from the study without experiencing the relevant event will be censored on the date of study completion/withdrawal.

Participants who prematurely withdraw from treatment but remain in the study will not be censored and will continue to be followed up until the first occurrence of the relevant event, study completion or withdrawal from the study.

Time to the relevant event will be calculated as:

$$\text{Time to event (days)} = \text{Date of event/censoring} - \text{date of randomization} + 1$$

5.3.3.6 Time to Discharge, Time to SpO2 ≥94% on Room Air and Time to Recovery

Time to discharge is defined as the time in days from randomization until the date of discharge.

Time to SpO2 ≥94% on room air is defined as the time in days from randomization to the first day at which an SpO2 measurement ≥94% on room air is reported after which there were no further requirements for oxygen therapy during the study.

Time to recovery is defined as the time in days from the date of symptom onset until the first day on which a WHO OSCI score of 0 is reported with no further increase above 0 during the study.

Participants who die during the study before the relevant event occurring will be given a status of 'death' which will be considered as a competing risk rather than an event or a censored observation in the analysis.

Participants who are still alive at the end of the 42-day study period or who withdraw prematurely from the study for reasons other than death without experiencing the relevant event will be censored on the date of study completion/withdrawal.

As the endpoint of SpO2 ≥94% on room air without further requirement for oxygen therapy cannot be measured after discharge (as SpO2 is not measured after discharge), any participants who have not achieved this before discharge will be considered as having met the endpoint criterion at the discharge date if they are discharged without oxygen for home use and will be censored at the discharge date if they are discharged with oxygen for home use. Note that these rules only apply for participants who are discharged before study completion/withdrawal.

Time to discharge and time to SpO2 will be calculated as:

$$\text{Time to event (days)} = \text{Date of event/censoring/death} - \text{date of randomization} + 1$$

Time to recovery will be calculated as:

$$\text{Time to event (days)} = \text{Date of event/censoring/death} - \text{date of symptom onset} + 1$$

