7.4 Lost to Follow Up

A participant will be considered lost to follow-up if he or she has been discharged or transferred to another hospital, and the study site is unable to contact the participant for their telephone visit.

Before a participant is deemed lost to follow-up, the investigator or designee must make every effort to regain contact with the participant by telephone. These contact attempts should be documented in the CRF.

If the participant continues to be unreachable after 3 attempts, he/she will be considered to have withdrawn from the study.

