8.1.4 Telephone call

If patients are discharged, they will be contacted by telephone on days 7, 14, 21 and 42 (+/- 1 day). The purpose of this call is to seek reporting of AEs, remind the participant to continue to fill their daily questionnaire (until symptoms have resolved or Day 42, whichever is sooner), and to offer the opportunity for any study-related questions.

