The difference in proportions between the treatment groups in the percentage of participants remaining at or below their baseline WHO OSCI score will be reported together with the corresponding 95% confidence interval at Days 4, 7, 10, 14, 21 and 42.

A CMH test for ordinal data will be used to compare the treatment groups with respect to the maximum WHO OSCI score recorded by each participant. Within each maximum score, the time in days spent at that score will also be summarised.

Overall survival will be analysed using a Cox proportional hazards (Cox-PH) model. The model will include parameters for treatment together with the additional baseline covariates which were identified during the blinded review of the overall survival model. Participants who are still alive at the end of the 42-day study period or who withdraw prematurely from the study for reasons other than death will be censored on the day of their study completion/withdrawal. The hazard ratio for treatment difference with corresponding 95% confidence interval will be presented.

If during the course of the study, a newly approved medication for COVID-19 becomes part of the standard of care treatment at the investigational site, a further sensitivity analysis will be performed. A time-dependent covariate for use of the new medication (yes, no) will be included in the model described above together with its interaction with treatment.

Intubation and mechanical ventilation free survival will be analysed in the same manner as described for overall survival above.

Number of days requiring oxygen therapy, number of days with pyrexia, maximum daily temperature, minimum and maximum SpO₂ values will be summarised only.

Time to discharge will be analyzed using the Fine and Gray subdistributional hazards model to allow for the competing risk of death (Fine 1999). The model will include parameters for treatment together with the additional baseline covariates which were identified during the blinded review of the time to discharge model.

Subjects who are not discharged and are still alive at the end of the 42-day study period or those who withdraw prematurely from the study without being discharged or dying will be censored on the day of study completion/withdrawal.

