5.3.3.4 WHO OSCI

The WHO OSCI has values ranging from 0 to 8 as shown in [Table 6](#).

Table 6 WHO Ordinal Scale for clinical Improvement

Participant State	Descriptor	Score
Uninfected	No clinical or virological evidence of infection	0
Ambulatory	No limitation of activities	1
	Limitation of activities	2

Participant State	Descriptor	Score
Hospitalized – Mild disease	Hospitalized, no oxygen therapy	3
	Oxygen by mask or nasal prongs	4
Hospitalized – Severe Disease	Non-invasive ventilation or high flow oxygen	5
	Intubation and mechanical ventilation	6
	Ventilation + additional organ support	7
Dead	Death	8

The WHO OSCI will be recorded daily in the eCRF while participants remain in hospital. Once discharged, the WHO OSCI will be derived from questions 1 and 2 of the daily COVID-19 diary using the rules defined in [Table 7](#).

Table 7 Derivation of WHO OSCI using the Outpatient Daily Covid-19 diary

Question 1: Overall, how severe were your COVID-19 symptoms today?	Question 2: How much did your COVID-19 symptoms interfere with your usual activities today?	WHO OSCI Score
No COVID-19 symptoms today	Any response	0
Mild, moderate, severe or very severe	Not at all	1
Mild, moderate, severe or very severe	Somewhat or Very much	2

For participants who report question 1 as “No COVID-19 symptoms today” and a return to their usual activities (Q3) for 2 days in a row do not need to complete the COVID-19 diary on subsequent days. If this condition is met, the missing WHO OSCI score will be imputed as 0 for any remaining study days up to and including Day 42.

Note that participants who are discharged on home oxygen will still be considered as having WHO OSCI score =2 as the participant state is considered before the descriptor in [Table 6](#).

For participants who die, the WHO OSCI score will be imputed to 8 for all remaining study days after death.

WHO OSCI scores that are missing for reasons other than death or full recovery of symptoms will not be imputed.

For the secondary endpoint looking at whether participants remained at or below their baseline WHO OSCI score at Days 4, 7, 10, 14, 21 and 42, participants who show an increased score and then return to their baseline score (or lower) will not be considered as having met the criterion for this endpoint. Only participants who have not reported a score above their baseline score on any day prior to the endpoint day will be considered as having met the endpoint for that day.

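### Time to recovery is censored at study completion even when the diary, its only outpatient source in the SAP, stopped earlier with symptoms still present

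*SAP*

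**What the plan says.** - **Event.** Time to recovery runs from symptom onset to the "first day on which a WHO OSCI score of 0 is reported with no further increase above 0 during the study" (SAP 5.3.3.6).
- **Source after discharge.** "Once discharged, the WHO OSCI will be derived from questions 1 and 2 of the daily COVID-19 diary" (SAP 5.3.3.4).
- **Permitted diary stop.** After two consecutive days without symptoms and with usual activities resumed, "the missing WHO OSCI score will be imputed as 0 for any remaining study days up to and including Day 42" (SAP 5.3.3.4).
- **Any other gap.** "WHO OSCI scores that are missing for reasons other than death or full recovery of symptoms will not be imputed" (SAP 5.3.3.4).
- **Censoring.** In both SAP 5.3.3.5 (survival) and 5.3.3.6 (recovery), participants who finish the 42 days or withdraw "without experiencing the relevant event will be censored on the date of study completion/withdrawal". SAP Table 13 repeats this for withdrawals. Protocol 9.4.1.2 says of overall survival that such participants "will be censored on the day of their study completion/withdrawal". It words time to discharge the same way and extends that analysis to recovery. At the 60-participant interim, SAP 9.3.4.1 and 9.3.5.1 use the data-cut date.
- **Contact after discharge.** Calls fall on Days 7, 14, 21 and 42, and "The purpose of this call is to seek reporting of AEs, remind the participant to continue to fill their daily questionnaire" (Protocol 8.1.4). The Schedule of Activities nevertheless lists the 8-point scale at Days 21 and 42.
- **Loss to follow-up.** "If the participant continues to be unreachable after 3 attempts, he/she will be considered to have withdrawn from the study" (Protocol 7.4). Neither document says which date is then recorded as the withdrawal date.

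**The concern.** Censoring tells the model how long a participant was seen to be event-free. For recovery, that knowledge ends with the last OSCI value. The plan carries it on to study completion, so every day after an early diary stop enters the Fine and Gray risk set as observed non-recovery.

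The SAP handles the same problem differently elsewhere. Because SpO2 is not measured after discharge, 5.3.3.6 settles the status for time to SpO2 ≥94% at the discharge date. Temperature (5.3.3.8) and oxygen days (5.3.3.7) each get a sensitivity variable. Time to recovery has the same observation gap and gets neither.

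The study is a pilot that is meant to compare endpoints for sensitivity and to inform the size of later trials. A recovery rate that is too low, or a distorted hazard ratio, would feed into that planning. The recovery table also goes to the DMC at the 60-participant efficacy review.

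**Working it through.** **1. The plan's own figures.** The only design figures are the confidence-interval half-widths in SAP Table 8. With t(0.975, N−2) × SD × √(4/N), all 18 entries reproduce; for N = 60 and SD 100 the result is 51.7. None bears on this point, and the plan states no recovery rate, event count or diary drop-out rate.

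**2. Who is affected.** The rules in SAP 5.3.3.4 and 5.3.3.6 combine as follows for a discharged participant who stays in the study:

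| Diary history | Treatment under the SAP |
|---|---|
| Stops after two symptom-free days with usual activities | Imputed 0; recovery event kept |
| Stops with last score 0, no later score | Recovery event kept |
| Stops with last score 1 or 2 | Censored at study completion |
| Never completes a diary | Censored at study completion |

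Only the last two rows are a problem.

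**3. Size for recovery.** All inputs here are assumptions. Recovery hazard r and diary drop-out hazard d are constant and independent, both clocks start at randomization, nobody dies (so Fine and Gray reduces to Cox), and all stay to Day 42.

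- True recovery by Day 42 = 1 − exp(−42r)
- Recovery reported under the plan = r/(r+d) × [1 − exp(−42(r+d))]

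*Moderate drop-out.* Median recovery is 14 days, so r = ln 2/14 = 0.0495. If a share s would have stopped by Day 42, d = −ln(1−s)/42. A simulation of 100,000 participants in whole days gave:

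| s | Stopped before recovery | Plan, Day 42 | Censored at last diary | True | Shortfall (points) |
|---|---|---|---|---|---|
| 10% | 4.2% | 84.5% | 87.5% | 87.5% | 3.0 |
| 20% | 8.5% | 81.5% | 87.5% | 87.5% | 6.0 |
| 30% | 13.0% | 78.1% | 87.4% | 87.5% | 9.4 |

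In an arm of 30, the second column is about 1.3 to 3.9 people (30 × 0.042 to 30 × 0.130). At s = 30% the plan gives 86.1% against 94.6% for a median of 10 days, and 65.9% against 75.0% for a median of 21 days.

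*Heavier drop-out.* With r = 0.05, truth is 1 − exp(−2.1) = 87.8%. With d = 0.005, 0.01 and 0.02 per day the plan reports 81.9%, 76.6% and 67.7%, a shortfall of about 6 to 20 points.

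*Later start.* The diary begins only at discharge. Starting both clocks at discharge on Day 7 or Day 14, with the same hazards, gives shortfalls of about 5 to 17 or 4 to 14 points.

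**4. Hazard ratio.**

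| Scenario (assumed) | True HR | Plan | Last-diary censoring |
|---|---|---|---|
| No effect, drop-out 10% on EDP1815 vs 30% on placebo | 1.00 | 1.12–1.14 | about 1.0 |
| No effect, d = 0.01 vs 0.02 per day | 1.00 | 1.21 | 1.00 |
| Effect present, d = 0.02 per day in both arms | 1.50 | 1.39 | 1.50 |

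With no effect and equal drop-out, both rules give about 1.0.

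**5. Survival endpoints.** Someone last reached on Day 21 and recorded as withdrawn after the failed Day 42 call adds 42 − 21 = 21 unobserved days. One to three such people in an arm of 30 add 21 to 63 of 30 × 42 = 1,260 person-days, or 1.7% to 5.0%.

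**The case against.** **Scope.** A reader might infer that all the time-to-event endpoints share this fault. The documents do not support that. Time to discharge does not depend on the diary, time to SpO2 ≥94% has its own discharge-date rules, and survival is known for anyone reached at Day 42. Nor does every diary stop count as non-recovery, as step 2 shows.

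**Other sources of status.** The Schedule of Activities lists the 8-point scale at Days 21 and 42, and its footnote on end-of-study record extraction covers symptoms. Later status may therefore exist. That is fair, but SAP 5.3.3.4 gives no rule for using it in outpatients, so the gap in the analysis remains.

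**Survival.** A reader might infer that lost participants are certainly credited with survival nobody saw. Because the withdrawal date is undefined, it could turn out to be the last contact, and mortality status may be found in the record. What stands is that the rule is undefined and that its possible effect is small.

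**Is last-diary censoring better?** It recovers the truth above only because drop-out was assumed unrelated to recovery. If, at 0.02 per day, those who stop do not recover by Day 42, the plan's 67.7% is right and last-diary censoring, at 87.8%, is 20 points too high. This stands, and it is why both analyses are needed.

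**Consequence.** Unequal drop-out in a blinded trial needs a mechanism, and none is documented. Assuming about 45 recoveries, the standard error of the log hazard ratio is about 2/√45 = 0.30. The shift from 1.50 to 1.39 is ln(1.50/1.39) = 0.076, a quarter of that. The analyses are secondary and descriptive, and diary compliance is tabulated by arm, so a marked imbalance would be visible. This limits the weight of the point but does not make the censoring date correct.

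**Conclusion.** The point holds for time to recovery. The SAP treats discharged participants who stop the diary with a last score above 0, or never complete one, as known not to have recovered up to Day 42. The estimated incidence of recovery is too low if any of them recover unseen. The shortfall is about 3 to 9 points at Day 42 for 10% to 30% assumed drop-out, and up to about 20 points under the heaviest rate tried. The hazard ratio is at risk mainly if drop-out differs by arm; equal drop-out can also pull a real effect towards 1.

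These sizes are illustrations. They rest on assumed drop-out and recovery rates, on drop-out unrelated to recovery and, except in the later-start check, on both clocks starting at randomization.

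For overall and ventilation-free survival the point is smaller. The withdrawal date of a lost participant needs a definition, since up to about 21 unobserved days per such participant may otherwise be counted.

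As these are descriptive secondary endpoints in a pilot, this is a correction that should be made, not a flaw that undermines the trial.

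**What to change.** 1. **SAP 5.3.3.6 and Table 13.** Censor time to recovery at the last day with an available OSCI value.
2. **SAP 5.3.3.4.** Allow the 8-point scale already scheduled at Days 21 and 42 as an outpatient source. State which date counts as recovery when a call gives a score of 0 after a diary gap, because the true date then lies somewhere in the gap.
3. **Sensitivity analysis.** Keep the present rule alongside, since the two rules make opposite assumptions about those who stop.
4. **SAP 5.3.3.5.** For lost participants, censor overall survival at the last date known alive, and ventilation-free survival at the last date known alive with OSCI below 6.
5. **SAP 9.3.4.1 and 9.3.5.1.** Apply the same dates at the 60-participant interim in place of the data-cut date.
6. **SAP section 14.** It now records no changes to the protocol. Enter this departure from Protocol 9.4.1.2 there.

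The cost is SAP wording and programming, with no new visits. The price in the analysis is more censoring, a somewhat wider interval for recovery, and a main analysis that relies on diary drop-out being unrelated to recovery.

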
To evaluate the effect of EDP1815 on length of hospitalization and recovery in participants with COVID-19	
Time to discharge, defined as the time in days from start of treatment to first occurrence of a WHO OSCI score of 2 or less.Time to oxygen saturation (SpO_2) $\geq 94\%$ on room air without further requirement for oxygen therapy.Time to recovery, defined as the time in days from symptom onset to alleviation of all COVID-19 symptoms.

To evaluate the safety and tolerability of EDP1815 in participants with COVID-19	
Incidence and severity of treatment emergent adverse events and serious adverse events.Incidence of clinically significant abnormal changes in safety laboratory parameters.
Exploratory	

To evaluate the effect of EDP1815 on the exaggerated host cytokine response to COVID-19 infection	
Change from baseline in cytokine levels (including IL-6) at day 4 and day 7 (and/or at additional timepoints if samples are available).Change from baseline in inflammatory response at day 4 and day 7 (and/or at additional timepoints if samples are available).

To identify clinical or biochemical predictors of response to EDP1815, and to confirm lack of systemic absorption.	
Statistical significance of each potential predictor-treatment interaction in exploratory models based on the final selected model for the primary efficacy analysis.To identify the presence of EDP1815 in stool and/or blood using PCR primers

4. Study Design

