8.6 Compliance

Treatment compliance will be summarized for the safety population and daily diary compliance will be summarized for the ITT population, by treatment group and overall.

Treatment and daily diary compliance data will also be listed.

9 Efficacy Analyses

Unless otherwise specified, all efficacy summaries and analyses will be presented by treatment group and overall. The ITT population will be used for all summaries and analyses of efficacy.

In addition to the inferential analyses described below, descriptive statistics will be provided to summarize all efficacy endpoints by treatment group.

For categorical variables, summary tabulations of frequency and percentage of participants within each category will be presented.

For continuous variables, the number of participants, mean, median, standard deviation (SD), minimum, and maximum values will be presented.

For time to event endpoints, the number of participants with the event, the number of participants censored will be presented together with Kaplan-Meier estimates of median time to event and the predicted proportion of subjects with the event at Days 4, 7, 14, 21 and 42 as appropriate to the endpoint. Kaplan-Meier curves of time to event will also be presented.

All analyses will be considered as descriptive only and no adjustment for multiple testing will be performed.

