9.3.5.2 Analytical Approach

Time to discharge will be analyzed using a Fine and Gray subdistributional hazards model to allow for the competing risk of death (Fine, 1999). The model will include a parameter for treatment together with any additional baseline covariates identified during the blinded review of the time to discharge model.

The number and percentage of participants who are discharged, who die and who are censored will be reported together the estimate of median time to the event, and the predicted proportion of participants who were discharged at Days 4, 7, 14, 21 and 42. The estimated subdistributional hazard ratio (with 95% confidence interval) for treatment difference in risk of recovery and its p-value from the model will also be presented. Cumulative incidence functions for time to full recovery will also be plotted by treatment group.

Time to discharge information will be listed including event status and time to event/censoring or death.

Time to SpO₂ ≥94% on room and time to recovery will be analyzed in the same manner as described above for time to discharge.

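### Time to recovery is counted from symptom onset without delayed entry, so pre-randomisation days enter the outcome and its medians, curves and landmark proportions are not on the study-day scale

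*SAP*

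**What the plan says.** - **Definition.** Protocol section 3, Table 2 (and Table 1 in the synopsis) gives "Time to recovery, defined as the time in days from symptom onset to alleviation of all COVID-19 symptoms". SAP 5.3.3.6 agrees: "Time to recovery is defined as the time in days from the date of symptom onset until the first day" on which OSCI 0 is reported with no later rise.
- **Formula.** In SAP 5.3.3.6, the line beginning "Time to recovery will be calculated as" subtracts the date of symptom onset from the date of event, censoring or death and adds 1. It contains no entry time.
- **Sister endpoints.** In the same section, "Time to discharge is defined as the time in days from randomization until the date of discharge". Time to SpO2 ≥94% on room air, overall survival and ventilation-free survival (SAP 5.3.3.5 and 5.3.3.6) also start at randomisation.
- **Model.** SAP 9.3.5.2: "Time to discharge will be analyzed using a Fine and Gray subdistributional hazards model to allow for the competing risk of death"; and "time to recovery will be analyzed in the same manner as described above for time to discharge".
- **Outputs.** SAP section 9 plans medians and "the predicted proportion of subjects with the event at Days 4, 7, 14, 21 and 42 as appropriate to the endpoint". SAP 9.3.5.2 repeats those days for time to discharge and adds cumulative incidence plots.
- **Covariate.** SAP 7.2 lists time since symptom onset among 15 candidates. Covariates are chosen by blinded forward selection at 5%, with at most 3 per model. SAP 9.1.1.2 extends this approach to the Fine and Gray models.

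**The concern.** Protocol 5.1 requires supplementary oxygen at baseline, and SAP 7.2 expects a baseline OSCI of 4 or 5. Recovery means OSCI 0. The interval from onset to randomisation is therefore event-free by design, yet the formula counts it as time at risk. No eligibility criterion limits symptom duration; the 36-hour limit in protocol 5.1 runs from admission. The interval can thus vary between participants, and all of that variation is added to the outcome.

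Protocol 4.1 names reducing time to resolution of symptoms as a study purpose, and this is the endpoint closest to it. Protocol 9.1 says the pilot should inform the sample size of future studies. Medians and curves that mix response after randomisation with lateness of presentation would be carried into that planning.

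**Working it through.** **1. The plan's own figure.** Neither document gives a precision or power figure for time to recovery. The only sample-size figures are the half-widths for trough S/F ratio in SAP Table 8. For N = 60 and SD = 100: t(0.975, 58) × SD × √(4/N) = 2.0017 × 100 × 0.2582 = 51.7, as stated. It does not bear on this endpoint.

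**2. What the formula does.** Let L be days from onset to randomisation and T the time counted from randomisation. The SAP formula gives T + L. Two participants who both recover at T = 10, with L = 4 and L = 14, are recorded as 14 and 24 days. A participant dosed on the day of randomisation and unrecovered at study Day 42 is censored at 42 + L, so the censoring horizon also differs between participants.

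**3. Assumptions.** The documents give no distribution for L. Protocol 2.1 places the exaggerated response, in a subgroup, 7-14 days after symptom onset. Means of 7-10 days and SDs of 2-6 days were tried.

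**4. Landmarks.** With gamma-distributed L (mean/SD 8/3, 8/5, 10/6), 78-94% of participants are not yet randomised on onset Day 4 and 50-64% on onset Day 7.

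**5. Chance imbalance.** With 30 per arm, the 95% range for the arm difference in mean L is ±2.00 × SD × √(2/30):

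| SD of L (days) | 95% range (days) |
|---|---|
| 2 | ±1.0 |
| 4 | ±2.1 |
| 6 | ±3.1 |

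**6. Fine and Gray simulation, constant hazard.** There were 60 participants, a control median of 16 days from randomisation, 8% at risk of death, no covariates, and 1,000 trials per setting (1,500 under the null).

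| True cause-specific HR | Randomisation clock: HR; rejection rate | Onset clock, no delayed entry: HR; rejection rate |
|---|---|---|
| 1.0 | 0.99-1.01; 4-6% | 0.99-1.01; 4-6% |
| 1.5 | 1.45-1.48; 25-28% | 1.44-1.48; 24-27% |
| 2.0 | 1.88-1.94; 60-63% | 1.85-1.93; 58-62% |

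The HR moves toward 1 by 0-3%, and power falls by 0-3 points. Left-truncating at randomisation on the onset clock brings the HR within 0.01 of the randomisation clock in each of these settings. Pre-randomisation days make up 38-51% of the measured time among those who recover. About 6-20% of an average risk set had not yet been randomised, and only about 2-10% of recoveries fall by onset Day 7.

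**7. Other hazard shapes.** These runs used Weibull recovery from randomisation, true HR 1.75, 60 participants and no deaths (so Cox equals Fine and Gray), with 500 trials per setting. The standard error of each power is about √(0.25/500) = 0.022.

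| Shape; control median; L mean/SD | Power, randomisation clock | Power, onset clock | Power, onset clock + time since onset | Time since onset passes 5% screen |
|---|---|---|---|---|
| 1.5; 12 d; 10/6 | 0.57 | 0.41 | 0.63 | 97% |
| 1.5; 12 d; 8/5 | 0.58 | 0.44 | 0.63 | 92% |
| 1.0; 20 d; 8/3 | 0.52 | 0.50 | not tabulated | 16% |

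The losses are 0.57 − 0.41 = 16 points, 0.58 − 0.44 = 14 points and 0.52 − 0.50 = 2 points. Repeat runs with rising hazard and wide spread gave losses of 11-17 points. In every setting run, adjusted power was within 1 point of the randomisation clock or higher. Adjusted HRs ran high, however (up to 1.92 against a true 1.75). Time since onset was also tested as the only candidate, without the other 14 competing for three places.

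**The case against.** The definition is deliberate. Protocol and SAP agree on it, and total illness duration is a coherent quantity. L is fixed before randomisation and so balanced in expectation. SAP 7.2 offers time since onset as a covariate, and it is most likely to be selected where the unadjusted loss is largest. SAP 8.3 tabulates time since onset by arm, so an imbalance would be visible. SAP 9.3.3 reports each OSCI level, including 0, at study Days 4, 7, 14, 21 and 42, so recovery status on the study clock is available. The landmark sentence in SAP section 9 is qualified by the endpoint. The trial is an unpowered pilot, and its analyses are called descriptive.

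Most of this stands, and it limits the weight of the point. It does not put this endpoint's medians and curves on the study scale. Selection of the covariate is also not assured. SAP 9.3.5.2 refers to covariates found in the time to discharge review and does not say whether recovery gets its own selection.

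A reader might infer a bias favouring one arm, because event-free time is counted. The documents do not support that: the interval precedes allocation in both arms, and the null simulations hold their level. A reader might also take the 17-point loss as the expected cost. It is an unadjusted result under assumed inputs and leaves out the planned covariate selection.

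**Conclusion.** The point holds as a design weakness in one secondary endpoint. It is not a contradiction between the documents and not a threat to the validity of the comparison. That pre-randomisation days count as time at risk, and that the time scale differs from time to discharge, follows from the text alone.

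The effect on the treatment comparison rests on assumptions about L and the recovery hazard. It is negligible with a narrow onset spread or in the constant-hazard settings with medians of 16-20 days. It reaches about 11-17 points of unadjusted power with a rising hazard, recovery soon after entry and a wide onset spread. Intermediate losses are possible between these. The loss is largely recovered if time since onset enters the model, which the plan permits but does not guarantee. The clearer and more certain harm is to the medians, cumulative incidence curves and landmark proportions.

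**What to change.** 1. In SAP 5.3.3.6, calculate time to recovery for the Fine and Gray model, medians, landmark proportions and cumulative incidence as date of event, censoring or death minus date of randomisation, plus 1, as for time to discharge.
2. In SAP 9.3.5.2, force time since symptom onset into the recovery model regardless of selection, and state whether it counts toward the limit of three.
3. In protocol Tables 1 and 2, and in SAP Table 1, which repeats them, give recovery the same origin wording that those tables use for time to discharge. That wording is start of treatment, so inserting randomisation for recovery alone would create a new mismatch.
4. Keep symptom-onset-to-recovery duration as a supplementary summary. If it is modelled, left-truncate at randomisation.

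The cost is one formula, the matching definitions and one forced covariate that is already collected. No new data are needed. The downside is that total illness duration becomes supplementary.
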